8. DATA MANAGEMENT

- For this study subject data will be entered into GSK defined eCRFs, transmitted electronically to GSK or designee and combined with data provided from other sources in a validated data system.
- Management of clinical data will be performed in accordance with applicable GSK standards and data cleaning procedures to ensure the integrity of the data, e.g., removing errors and inconsistencies in the data.

- Adverse events and concomitant medications terms will be coded using MedDRA (Medical Dictionary for Regulatory Activities) and an internal validated medication dictionary, GSKDrug.
- eCRFs (including queries and audit trails) will be retained by GSK, and copies will be sent to the Investigator to maintain as the Investigator copy. Subject initials will not be collected or transmitted to GSK according to GSK policy.

9. STATISTICAL CONSIDERATIONS AND DATA ANALYSES

9.1. Hypotheses

The primary objective of this study is to evaluate the efficacy and safety of UMEC in combination with FF/VI in subjects with asthma over a 24 week treatment period. This is a superiority study to demonstrate the add-on benefit of UMEC at two dosage strengths 62.5 mcg and 31.25 mcg in a single inhaler when compare to FF/VI. The primary efficacy endpoint is the mean change from baseline in trough FEV₁ at the end of the 24-week treatment period.

For each test on each efficacy endpoint, the null hypothesis is that there is no difference between treatment groups.

$$H_0: T_1 - T_2 = 0$$

The alternative hypothesis is that there is a difference between treatment groups.

$$H_1: T_1 - T_2 \neq 0$$

For the primary endpoint and other lung function related efficacy endpoints, the primary treatment comparisons of interest are the comparisons for each triple therapy and the respective dual therapy FF/VI without the UMEC component as follows:

UMEC 62.5 mcg:

- FF/UMEC/VI 100/62.5/25 mcg vs. FF/VI 100/25 mcg
- FF/UMEC/VI 200/62.5/25 mcg vs. FF/ VI 200/25 mcg

UMEC 31.25 mcg:

- FF/UMEC/VI 100/31.25/25 mcg vs. FF/VI 100/25 mcg
- FF/UMEC/VI 200/31.25/25 mcg vs. FF/ VI 200/25 mcg

Therefore T₁ and T₂ for these endpoints are the mean changes from baseline for the individual triple therapy and dual therapy, respectively, as listed above.

For the key secondary endpoint and all other non-lung function efficacy endpoints, the primary treatment comparisons of interest are the comparisons between triple therapy and dual therapy for a fixed dose of UMEC:

- (FF/UMEC/VI 100/62.5/25, 200/62.5/25) vs. (FF/VI 100/25, 200/25)
- (FF/UMEC/VI 100/31.25/25, 200/31.25/25) vs. (FF/VI 100/25, 200/25)

For example, T_1 and T_2 in the hypothesis associated with the key secondary efficacy endpoint are the averages of the mean annualized rate of moderate/severe exacerbations for the triple therapies over two FF doses at a given UMEC dose, and for the dual therapies over two FF doses, respectively.

Details on all pairwise treatment comparisons of interest are provided in Section 9.3.3.

9.2. Sample Size Considerations

9.2.1. Sample Size Assumptions

Sample size calculation is based on the primary efficacy endpoint of mean change from baseline in trough FEV₁ at the end of the 24-week treatment period.

A total of 2250 randomized subjects are required for this study, with 375 subjects in each of the six double-blind treatment groups:

- FF/VI 100/25 mcg
- FF/VI 200/25 mcg
- FF/UMEC/VI 100/31.25/25 mcg
- FF/UMEC/VI 200/31.25/25 mcg
- FF/UMEC/VI 100/62.5/25 mcg
- FF/UMEC/VI 200/62.5/25 mcg

Assuming 10% missing data on spirometry at the end of the 24-week treatment period, due to early withdrawal from study, approximately 337 subjects per treatment group should have trough FEV₁ data available for the analysis.

The standard deviation for the mean change from baseline in trough FEV₁ at the end of the 24-week treatment period is estimated to be 400 mL based on previous asthma studies. The proposed sample size of n=337 per treatment group should provide 90% power, assuming a difference of 100 mL, based on a two sample t-test with a two sided significance level of 0.05 for each of the two primary comparisons of interest for each UMEC dose.

For the target population, it is assumed that the mean exacerbation rate is 2 per year for the control group FF/VI; this was based on a review of previous FF/VI asthma exacerbation study conducted by GSK and Tio asthma studies conducted by Boehringer Ingelheim. The proposed sample size of 750 randomized subject per arm (based on the treatment comparison of combined triple therapies and combined dual therapies with both FF doses) should have approximately 95% power if the true reduction in exacerbation

rate for triple therapy vs. dual therapy is 20%. The calculation assumes the number of exacerbations per year follows a negative binomial distribution [Keene 2007], with a dispersion parameter $k=0.7$ based on a previous FF/VI asthma exacerbation study, and assumes the following accelerative recruitment rate per week over a period of 39 weeks:

[figure not shown]
- 3.5 weeks at 15 patients/week
- 4.5 weeks at 25 patients/week
- 4.5 weeks at 35 patients/week
- 4.5 weeks at 45 patients/week
- 4.5 weeks at 55 patients/week
- 4.5 weeks at 70 patients/week
- 13 weeks at 90 patients/week

The duration of the treatment period is variable but will be at least 24 weeks and up to a maximum of 52 weeks, with the end of study date being established once the last subject has been randomized.

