9.3.4. Multiple Comparisons and Multiplicity

In order to account for multiple tests involving two UMEC doses and across multiple efficacy endpoints, a step-down testing procedure will be applied whereby inference for a test in the pre-defined hierarchy is dependent upon statistical significance having been achieved for the previous tests in the hierarchy.

A step-down closed testing approach will be applied for the primary efficacy endpoint, the key secondary efficacy endpoint, and the secondary efficacy endpoints SGRQ, ACQ-7, and E-RS. Specifically, if the defined treatment comparisons for the primary efficacy endpoint between triple therapy and dual therapy at the high dose of UMEC 62.5 mcg are statistically significant at the 0.05 level for both fixed FF doses (100 and 200mcg), then the replicate efficacy of UMEC 62.5mcg is demonstrated, and the defined treatment comparison between triple therapy and dual therapy will be tested for the key secondary efficacy endpoint of moderate/severe asthma exacerbations based on the combined data of both FF doses for UMEC 62.5mcg. If the test for the key secondary efficacy endpoint is statistically significant at the 0.05 level, then the secondary efficacy endpoints for SGRQ (Mean change from baseline in SGRQ at Week 24) and ACQ-7 (Mean change from baseline in ACQ-7 at Week 24) will be tested sequentially based on the combined data of both FF doses for UMEC 62.5mcg at significance level 0.05.

If all tests mentioned above for UMEC 62.5 mcg are statistically significant at the 0.05 level, the above testing hierarchy for the primary efficacy endpoint, the key secondary efficacy endpoint, and the secondary efficacy endpoints SGRQ and ACQ-7 will be repeated for the low dose of UMEC 31.25 mcg.

If all tests for the primary, the key secondary, and the secondary efficacy endpoints for SGRQ and ACQ-7 are statistically significant at the 0.05 level for both UMEC 62.5mcg and 31.25mcg, the secondary endpoint for E-RS (Mean change from baseline in E-RS score over the Weeks 21-24 (inclusive) of the treatment period) will be tested at the significance level 0.05 for UMEC 62.5 and UMEC 31.25 in sequence.

The family-wise Type I Error is strongly controlled at 0.05 level for both UMEC 62.5mcg and UMEC 31.25mcg on the primary endpoint (trough FEV1), the key secondary endpoint (moderate/severe asthma exacerbations), and the secondary endpoints on SGRQ, ACQ-7, and E-RS.

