All secondary non-lung function efficacy endpoints will be tested for triple vs. dual using the combined data of both FF doses, at a given UMEC dose. The full testing hierarchy is provided below:

Multiplicity Adjustment Plan

Level 1: Primary endpoint, UMEC 62.5 mcg: Mean change from baseline in trough FEV1 at Week 24,

Two comparisons:

FF/UMEC/VI 100/62.5/25 vs. FF/VI 100/25

FF/UMEC/VI 200/62.5/25 vs. FF/VI 200/25

Both tests need to be significant at 0.05 level in order to demonstrate replicate efficacy for UMEC 62.5 mcg in order to move to Level 2 test.

Level 2: Key secondary endpoint, UMEC 62.5 mcg: Annualized rate of moderate/severe asthma exacerbations,

One comparison based on pooled data:

(FF/UMEC/VI 100/62.5/25, 200/62.5/25) vs. (FF/VI 100/25, 200/25)

Test needs to be significant at 0.05 level in order to move to Level 3 test.

Level 3: Secondary endpoint, UMEC 62.5 mcg: Mean change from baseline in SGRQ at Week 24,

One comparison based on pooled data:

(FF/UMEC/VI 100/62.5/25, 200/62.5/25) vs. (FF/VI 100/25, 200/25)

Test needs to be significant at 0.05 level in order to move to Level 4 test.

Level 4: Secondary endpoint, UMEC 62.5 mcg: Mean change from baseline in ACQ-7 at Week 24,

One comparison based on pooled data:

(FF/UMEC/VI 100/62.5/25, 200/62.5/25) vs. (FF/VI 100/25, 200/25)

Test needs to be significant at 0.05 level in order to move to Level 5 tests.

Level 5: Primary endpoint, UMEC 31.25mcg: Mean change from baseline in trough FEV1 at Week 24,

Two comparisons:

FF/UMEC/VI 100/31.25/25 vs. FF/VI 100/25

FF/UMEC/VI 200/31.25/25 vs. FF/VI 200/25

Both tests need to be significant at 0.05 level in order to demonstrate replicate efficacy for UMEC 31.25mcg and move to Level 6 test.

Level 6: Key secondary endpoint, UMEC 31.25 mcg: Annualized rate of moderate/severe asthma exacerbations,

One comparison based on pooled data:

(FF/UMEC/VI 100/31.25/25, 200/31.25/25) vs. (FF/VI 100/25, 200/25)

Test needs to be significant at 0.05 level in order to move to Level 7 test.

Level 7: Secondary endpoints, UMEC 31.25 mcg: Mean change from baseline in SGRQ at Week 24.

One comparison based on pooled data:

(FF/UMEC/VI 100/31.25/25, 200/31.25/25) vs. (FF/VI 100/25, 200/25)

Test needs to be significant at 0.05 level in order to move to Level 8 test.

Level 8: Secondary endpoint, UMEC 31.25 mcg: Mean change from baseline in ACQ-7 at Week 24.

One comparison based on pooled data:

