#### 5.4. Multi-Centre Studies

Due to the large number of centers participating in this study, a geographical region will be used rather than adjusting for center in the statistical analyses. The center grouping will be created based on geographical region and number of randomized participants in a country, in order to define groups of roughly similar size.

Geographic Region	Countries	Total # Randomized / Planned
Europe	Germany, Italy, Netherlands, Poland, Romania, Spain, United Kingdom,	766 / 575
Russia	Russian Federation	643 / 500
United States	United States	399 / 400
Rest of World	Argentina, Australia, Canada, Japan, Republic of Korea, South Africa	631 / 735

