## Multiplicity Adjustment Plan

Level 1: Primary endpoint, UMEC 62.5 mcg: Mean change from baseline in trough FEV1 at Week 24,

Two comparisons:

FF/UMEC/VI 100/62.5/25 vs. FF/VI 100/25

FF/UMEC/VI 200/62.5/25 vs. FF/VI 200/25

Both tests need to be significant at 0.05 level in order to demonstrate replicate efficacy for UMEC 62.5 mcg in order to move to Level 2 test.

Level 2: Key secondary endpoint, UMEC 62.5 mcg: Annualized rate of moderate/severe asthma exacerbations,

One comparison based on pooled data:

(FF/UMEC/VI 100/62.5/25, 200/62.5/25) vs. (FF/VI 100/25, 200/25)

Test needs to be significant at 0.05 level in order to move to Level 3 test.

Level 3: Secondary endpoint, UMEC 62.5 mcg: Mean change from baseline in SGRQ at Week 24,

One comparison based on pooled data:

(FF/UMEC/VI 100/62.5/25, 200/62.5/25) vs. (FF/VI 100/25, 200/25)

Test needs to be significant at 0.05 level in order to move to Level 4 test.

Level 4: Secondary endpoint, UMEC 62.5 mcg: Mean change from baseline in ACQ-7 at Week 24,

One comparison based on pooled data:

(FF/UMEC/VI 100/62.5/25, 200/62.5/25) vs. (FF/VI 100/25, 200/25)

Test needs to be significant at 0.05 level in order to move to Level 5 tests.

Level 5: Primary endpoint, UMEC 31.25mcg: Mean change from baseline in trough FEV1 at Week 24,

Two comparisons:

FF/UMEC/VI 100/31.25/25 vs. FF/VI 100/25

FF/UMEC/VI 200/31.25/25 vs. FF/VI 200/25

Both tests need to be significant at 0.05 level in order to demonstrate replicate efficacy for UMEC 31.25mcg and move to Level 6 test.

Level 6: Key secondary endpoint, UMEC 31.25 mcg: Annualized rate of moderate/severe asthma exacerbations,

One comparison based on pooled data:

(FF/UMEC/VI 100/31.25/25, 200/31.25/25) vs. (FF/VI 100/25, 200/25)

Test needs to be significant at 0.05 level in order to move to Level 7 test.

Level 7: Secondary endpoints, UMEC 31.25 mcg: Mean change from baseline in SGRQ at Week 24.

One comparison based on pooled data:

(FF/UMEC/VI 100/31.25/25, 200/ 31.25/25) vs. (FF/VI 100/25, 200/25)

Test needs to be significant at 0.05 level in order to move to Level 8 test.

Level 8: Secondary endpoint, UMEC 31.25 mcg: Mean change from baseline in ACQ-7 at Week 24.

One comparison based on pooled data:

(FF/UMEC/VI 100/31.25/25, 200/ 31.25/25) vs. (FF/VI 100/25, 200/25)

Test needs to be significant at 0.05 level in order to move to Level 9 test.

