
 
• Baseline summaries will be presented for all participants, those who are on-treatment at week 24 and those who are off-treatment at week 24 and for those who are missing data at week 24.
 
• Data collected at all scheduled clinic visits, both on- and post-treatment, will be summarized by visit (absolute value and change from baseline).
 
• Boxplots of the change from baseline at each clinic visit will be presented.
 
• Empirical distribution function plots of the change from baseline at each clinic visit will be presented.
 
• Least-square (LS) means and LS mean change from baseline values for each treatment group will be presented with their associated standard errors. The estimated treatment difference along with corresponding standard error, 95% CI and unadjusted p-value will be presented for all treatment comparisons specified in Section 7 at Weeks 4, 12, and 24.
 
• LS mean change from baseline values and LS mean treatment differences (and associated 95% CIs) for the comparisons of the two FF/UMEC/VI vs. a FF/VI at a given FF dose will be presented graphically at Weeks 4, 12, and 24, for each of the FF doses in two separate panels.
 

Exploring interaction terms

 
• Interaction by treatment terms will added to the main model one at a time for the following main effect covariates: age, baseline value for clinic FEV1, region, sex and pre-study ICS dosage at screening.
 
• Summary of test results for main effect covariates in main model will be presented along with the test results for the interaction terms mentioned above.
 

Primary Statistical Analyses
Supportive Statistical Analyses

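### Does the 90% power in Protocol 9.2.1 need restating as the power to win under the testing hierarchy?

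*Protocol*

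**What the plan says.** Protocol 9.2.1 assumes 375 randomized per arm and 10% missing Week 24 spirometry, hence about 337 evaluable. That number "should provide 90% power, assuming a difference of 100 mL", "based on a two sample t-test with a two sided significance level of 0.05". The scope of the claim is given in the same sentence: "with a two sided significance level of 0.05 for each of the two primary comparisons of interest for each UMEC dose". The FEV1 table in Section 9.2.2 gives the power of a single comparison over a range of differences and SDs.

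Protocol 9.3.4 then sets the decision rule. At Level 1, "Both tests need to be significant at 0.05 level in order to demonstrate replicate efficacy for UMEC 62.5 mcg". Levels 2 to 4 are the pooled exacerbation, SGRQ and ACQ-7 tests for 62.5 mcg. The lower dose comes next: "If all tests mentioned above for UMEC 62.5 mcg are statistically significant at the 0.05 level, the above testing hierarchy" is repeated for 31.25 mcg. SAP 5.6 carries the same hierarchy, and its Level 5 reads "Both tests need to be significant at 0.05 level in order to demonstrate replicate efficacy for UMEC 31.25mcg and move to Level 6 test". The SAP has no sample size section, and neither document reports a joint power.

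Outside the hierarchy, SAP 7.1.6 states that the "95% CI and unadjusted p-value will be presented for all treatment comparisons specified in Section 7".

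**The concern.** The trial aims to show the add-on benefit of UMEC at two strengths, and Section 9.2.1 attaches the same 90% to both. The confirmatory claim at either dose, however, needs two FEV1 tests to succeed, and the claim at 31.25 mcg needs every earlier 62.5 mcg test to succeed as well. Someone who read 9.2.1 without 9.3.4 could take 90% as the chance of a formal FEV1 claim at each dose.

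If that reading were natural, the chance of missing Level 1 would be understated (about 19% against 10%). The chance of missing replicate efficacy at 31.25 mcg would be understated further (at least about 31% on the planning inputs). The 31.25 mcg input is also the less secure one. Protocol 4.5 says the Phase IIb study did not include that dose, yet 9.2.1 uses 100 mL for both.

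**Working it through.** **Inputs.** From Protocol 9.2.1: difference 100 mL, SD 400 mL, n = 337 per arm (375 × 0.90 = 337.5), two-sided 0.05, two-sample t-test. From Protocol 9.3.4: the both-must-win rule at each dose and the Level 5 position of 31.25 mcg. Both UMEC doses are given a true effect of 100 mL, as 9.2.1 does.

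**1. The plan's own figure.**
- SE of a difference = 400 × √(2/337) = 30.8 mL.
- Noncentrality = 100/30.8 = 3.245.
- Normal approximation: Φ(3.245 − 1.960) = Φ(1.285) = 0.901. Noncentral t with 672 df: 0.900.

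The stated 90% reproduces. Every cell of the FEV1 table in 9.2.2 also reproduces by noncentral t to within 0.01.

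**2. Replicate efficacy at 62.5 mcg (Level 1).** The FF 100 and FF 200 comparisons use different arms, so they are independent: 0.900² = 0.81.

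**3. FEV1 tests needed for 31.25 mcg (Levels 1 and 5).** Within an FF stratum the two UMEC arms share one FF/VI control. The two differences have variance 2σ²/n each and covariance σ²/n, so their correlation is 0.5.
- P(both significant in one stratum), bivariate normal with correlation 0.5: 0.833.
- Both 62.5 mcg tests plus one 31.25 mcg test: 0.833 × 0.901 = 0.75.
- All four FEV1 tests: 0.833² = 0.69.

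Simulation of 400,000 trials gave 0.81 for step 2 and 0.69 for all four tests. Treating the four tests as independent would give 0.901⁴ = 0.66, which is too low.

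The results in step 3 are upper bounds for 31.25 mcg on these inputs, because Levels 2 to 4 can only remove successes.

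**4. How stable the joint figures are.** n = 337 unless noted.

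| Scenario | One comparison at 62.5 mcg | Both 62.5 mcg | All four FEV1 |
|---|---|---|---|
| 100 mL, SD 400 mL (planned) | 0.90 | 0.81 | 0.69 |
| 90 mL, SD 400 mL | 0.83 | 0.69 | 0.53 |
| 110 mL, SD 400 mL | 0.95 | 0.89 | 0.82 |
| 100 mL, SD 375 mL | 0.93 | 0.87 | 0.78 |
| 100 mL, SD 350 mL | 0.96 | 0.92 | 0.86 |
| 100 mL, SD 425 mL | 0.86 | 0.74 | 0.60 |
| 100 mL at 62.5 mcg, 80 mL at 31.25 mcg | 0.90 | 0.81 | 0.49 |
| 136 mL at 62.5 mcg, 100 mL at 31.25 mcg | 0.99 | 0.99 | 0.81 |
| 100 mL, SD 400 mL, n = 366 | 0.92 | 0.85 | 0.75 |

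The effects of 80 to 110 mL and the SDs of 350 to 425 mL lie within the 9.2.2 grid. The 136 mL is the Phase IIb result in Protocol 4.5 (four weeks, against FF alone, so not directly transferable). The n = 366 comes from the table in SAP 5.4 headed "Total # Randomized / Planned": 766 + 643 + 399 + 631 = 2439 randomized, and 2439/6 × 0.90 = 366.

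**The case for a change.** The best argument for a change is that power should be stated for the criterion the trial will be judged by. The sponsor accepted a similar principle for exacerbations: Amendment 1 recalculated that power when the truncated visit schedule changed the exposure. Two sentences in 9.2.1 would do the same for FEV1, and would help a reader interpret a 31.25 mcg comparison that was never formally tested because an earlier gate failed. The higher enrolment does not remove the gap either, since the joint figures at n = 366 are still below 90%.

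The arithmetic stands, and so does the observation that no joint power is printed. The case for treating this as a defect is weaker, for three reasons.

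- The sentence in 9.2.1 already says which tests the 90% covers, so half of the suggested text would repeat it.
- The suggested bound of 69% belongs to an unadjusted t-test. The planned primary analysis is an MMRM adjusted for baseline, age, sex, region and pre-study ICS dosage, using the earlier visits of subjects who withdraw. If that brings the effective SD to 375 mL, the figure is 78%. The documents do not quantify this gain, and a weaker effect at 31.25 mcg would push the other way.
- The added figure would still stop short of the actual 31.25 mcg rule. Section 9.2.2 tabulates 0.92 for the pooled exacerbation test (control rate 2, 20% reduction, dispersion 0.7), but SGRQ and ACQ-7 have no planning values, so power through Level 5 cannot be computed from the documents.

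**Conclusion.** No change is needed. The 90% is numerically right and correctly scoped, and the hierarchy is set out in full in both documents. Requiring both tests costs power but does not inflate the type I error. A statistician who wants the joint figures can derive them from what is written: about 81% for replicate efficacy at 62.5 mcg and about 69% for all four FEV1 tests, given 100 mL at both doses, SD 400 mL, 337 evaluable per arm and an unadjusted t-test, before the exacerbation, SGRQ and ACQ-7 gates.

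Printing them would be an optional clarification with no effect on the trial. Sample size, tests, order of testing and analysis would stay as they are. The SAP already records 2439 subjects randomized, so revised planning text could not alter the design. Estimates, confidence intervals and unadjusted p-values are reported for every comparison wherever the hierarchy stops. The joint figures run from about 49% to 86% for all four FEV1 tests over the inputs tabulated above, so a single number in 9.2.1 would carry little weight without its assumptions.

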
 • In Section 7.3.5, Section 7.3.6, Section 7.5.1.2 and Section 7.5.8, the description of the data collected on the Medical Problems/Medications Taken worksheet has been revised to allow for the collection of data related to study treatment (as well as non-study treatment). • In Section 7.3.6, instructions for collecting the occurrence of asthma exacerbations in the electronic Case Report Form (eCRF) have been included. • In Section 7.5.2, a blank row in the provided table has been deleted. • In Section 7.5.6, the timing of the ECG assessments has been clarified. • In Section 7.6, the order of assessments has been amended. • In Section 9.2.2, the power for the key secondary endpoint (and associated graphs) has been re-calculated and updated. • In Section 9.3.4, Level 3b and Level 5 of the Multiplicity Adjustment Plan have been updated to amend the wording of the ‘mean change from baseline in E-RS score’ endpoint (in order to align with the associated amendments made in Section 3 and Section 7.3.1.3). • In Section 9.4, a typographical error has been corrected. 		
2016N271022_03	2017-JUN-23	Amendment No. 2

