5.7. Subject and Study Completion

The date that the whole study will complete (henceforth referred to as the study completion date) will be determined based on the randomization date of the final subject in the study; the study completion date will be set at 181 days (i.e. 25 weeks and 6 days) post the final subject's randomization date.

To determine when the final treatment/EOS visit will occur for each randomized subject in this variable duration study (i.e. at Week 24, Week 36 or Week 52 of the treatment period), a date henceforth referred to as the transition date will be communicated to the study sites by GSK. GSK will communicate a *provisional* transition date to all study sites on an ongoing basis during the study, until a fixed *actual* transition date is communicated at least 20 weeks in advance of the selected date (unless extenuating circumstances dictate otherwise). The date selected by GSK as the actual transition date will always be more than 12 days prior to the study completion date. At the Investigator's discretion, subjects should be informed of the transition date (provisional and actual) on an ongoing basis during the study so that their expected final treatment/EOS visit can be planned using the provisional transition date and then confirmed once the actual transition date is known.

Subjects who complete 52 weeks of study treatment prior to the actual transition date being communicated will have their final treatment/EOS visit at their Week 52 clinic assessment visit.

After the actual transition date is communicated, subjects must adhere to their study visit schedule and complete a minimum of 24 weeks of study treatment. A subject's final treatment/EOS visit will be defined as follows:

- Subjects whose Week 24 clinic assessment visit is scheduled to occur on or after the actual transition date (without consideration of available visit time-windows) will have their final treatment/EOS visit at their Week 24 clinic assessment visit.
- Subjects who have their Week 24, Week 36 or Week 52 clinic assessment visit scheduled to occur before the actual transition date (without consideration of available visit time-windows) will have their final treatment/EOS visit at the clinic assessment visit that is scheduled to occur before but closest to the actual transition date (without consideration of available visit time-windows).

The subject's final treatment/EOS visit must include all assessments specified for Visit 8/EOS.

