9.2.2. Sample Size Sensitivity

To demonstrate the sensitivity of the sample size calculation for this study, the following table and graph show the power function for a fixed sample size of $n=337$ per arm in the ITT population for the primary efficacy analysis, varying the observed treatment difference and estimated standard deviation on the change from baseline in trough FEV_1 at the end of the 24-week treatment period.

Standard Deviation	Treatment difference (mL)				
	80	90	100	110	120
350	0.84	0.92	0.96	0.98	0.99
375	0.79	0.88	0.93	0.97	0.99
400	0.74	0.83	0.90	0.95	0.97
425	0.69	0.78	0.86	0.92	0.96
450	0.64	0.74	0.82	0.89	0.93

[figure not shown]
[figure not shown]

For the key secondary endpoint, the following table shows the power function for a fixed sample size of n=750 per arm (combining two FF containing triple arms or dual arms for a fixed UMEC dose) or for a fixed sample size of n=375 per arm (individual treatment group) in the ITT population, varying the mean annualized rate of exacerbations in the control group, the true treatment effect (relative reduction in moderate/severe exacerbations) and the dispersion assumption in a variable duration study, assuming an

accelerative recruitment rate per week over a period of 39 weeks as given in Section 9.2.1.

dispersion	FF/VI rate	FF/UMEC/VI rate	Relative Reduction	power	
				n=750/arm	n=375/arm
0.7	1.50	1.275	15%	0.62	0.37
	1.50	1.200	20%	0.87	0.59
	1.50	1.125	25%	0.98	0.81
	2.00	1.700	15%	0.70	0.41
	2.00	1.600	20%	0.92	0.67
	2.00	1.500	25%	0.99	0.87
	2.50	2.125	15%	0.75	0.49
	2.50	2.000	20%	0.95	0.72
	2.50	1.875	25%	>0.99	0.90
0.8	1.50	1.275	15%	0.61	0.36
	1.50	1.200	20%	0.86	0.56
	1.50	1.125	25%	0.97	0.77
	2.00	1.700	15%	0.65	0.41
	2.00	1.600	20%	0.91	0.66
	2.00	1.500	25%	0.99	0.85
	2.50	2.125	15%	0.73	0.44
	2.50	2.000	20%	0.94	0.69
	2.50	1.875	25%	>0.99	0.88

The power for the statistical test on the key secondary efficacy endpoint was further evaluated for a fixed UMEC dose, assuming a constant rate of recruitment at 40, 50, or 75 subjects per week throughout the enrolment period. The power functions were illustrated below for n=750/arm and n=375/arm, respectively, assuming dispersion=0.7 and a mean annualized rate of moderate/severe exacerbations of 2 for FF/VI group.

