	2.00	1.500	25%	>0.99	0.87																																																																																																																								
	2.50	2.125	15%	0.76	0.47																																																																																																																								
	2.50	2.000	20%	0.95	0.73																																																																																																																								
	2.50	1.875	25%	>0.99	0.91																																																																																																																								

Change Section, Text affected, and Rationale

Change Section, Text affected, and Rationale

[figure not shown]

Changed to:

[figure not shown]
dispersion	FF/VI rate	FF/UMEC/VI rate	Relative Reduction	power					
				n=750/arm	n=375/arm				
0.7	1.50	1.275	15%	0.6662	0.4037				
			20%	0.9087	0.6359				
			25%	0.98	0.8481				
	2.00	1.700	1.600	15%	0.7370	0.4541			
				20%	0.9492	0.7267			
				25%	≥0.99	0.8987			
				2.50	2.125	1.875	15%	0.7775	0.5049
							20%	0.9795	0.7672
							25%	>0.99	0.9390
				0.8	1.50	1.275	15%	0.6261	0.4036

Change Section, Text affected, and Rationale

	1.50	1.200	20%	0.8886	0.6456
	1.50	1.125	25%	0.9997	0.8277
	2.00	1.700	15%	0.7065	0.4541
	2.00	1.600	20%	0.9391	0.6566
	2.00	1.500	25%	≥0.99	0.8785
	2.50	2.125	15%	0.7673	0.4744
	2.50	2.000	20%	0.9594	0.7369
	2.50	1.875	25%	>0.99	0.9188

Change Section, Text affected, and Rationale

Rationale: To capture the change to the power calculation based on the proposed study duration that is truncated to the scheduled visits at Weeks 24, 36 and 52. The original power calculation was based on the variable duration up to Week 52.

32. Section 9.3.4 Multiple Comparisons and Multiplicity: Multiplicity Adjustment Plan, level 3b AND level 5, mean change from baseline in E-RS total score endpoint:

Changed from:

Mean change from baseline in E-RS score over the 24 week treatment period

- a. (FF/UMEC/VI 100/62.5/25, 200/62.5/25) vs. (FF/VI 100/25, 200/25)

Changed to:

Mean change from baseline in E-RS score over **Weeks 21 to 24 (inclusive) of the 24-week** treatment period

- a. (FF/UMEC/VI 100/62.5/25, 200/62.5/25) vs. (FF/VI 100/25, 200/25)

Rationale: To align the Multiplicity Adjustment Plan with the Other Secondary endpoints.

33. Section 9.4 Key Elements of Analysis Plan: second paragraph, third sentence:

Changed from:

Change	Section, Text affected, and Rationale

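### Protocol Section 9.2.1 states about 95% power for the exacerbation endpoint, but the Section 9.2.2 table gives 0.92 for the same inputs

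*Protocol*

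**What the plan says.** Protocol Section 9.2.1 sizes the trial on trough FEV1 and then gives power for the key secondary endpoint. It assumes that the "mean exacerbation rate is 2 per year for the control group FF/VI", that the exacerbation count is negative binomial with dispersion 0.7, that 750 subjects per arm are compared after pooling the two FF doses, and that accrual accelerates in steps over 39 weeks. On these inputs the trial "should have approximately 95% power if the true reduction in exacerbation" "rate for triple therapy vs. dual therapy is 20"%. The section describes treatment duration only as variable, between 24 and 52 weeks.

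Section 9.2.2 tabulates power for the same endpoint and refers back to Section 9.2.1 for accrual. At dispersion 0.7 the row for a control rate of 2.00 reads "2.00 1.600 20% 0.92 0.67", where the last two figures are power at 750 and at 375 per arm. Among the 20% rows at dispersion 0.7, the value 0.95 appears only at a control rate of 2.50: "2.50 2.000 20% 0.95 0.72".

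Section 5.7 fixes when follow-up ends "in this variable duration study (i.e. at Week 24, Week 36 or Week 52 of the treatment period").

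**The concern.** Two sections of the protocol in force give different power for the same sample size, control rate, reduction, dispersion and accrual. They cannot both describe the trial as designed. The exacerbation comparison is Level 2 of the testing hierarchy for UMEC 62.5 mcg and Level 6 for UMEC 31.25 mcg (Section 9.3.4), and a failure at either level stops all later testing. A reader who stops at Section 9.2.1 takes away too favourable a figure for that gate.

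The amendment history suggests the cause, and I use it only for that. The summary of changes for Amendment 1 records: "In Section 9.2.2, the power for the key secondary endpoint (and associated graphs) has been re-calculated and updated". It does not name Section 9.2.1. The rationale in Appendix 8 describes the change as a "power calculation based on the proposed study duration that is truncated to the scheduled visits at Weeks 24, 36 and 52", and says the earlier calculation used the variable duration up to Week 52. It appears that the table was brought into line with the visit-based follow-up and the sentence in Section 9.2.1 was not.

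**Working it through.** **Inputs.** From Sections 9.2.1 and 9.2.2: n = 750 per pooled arm; rates 2.0 and 1.6 per year (ratio 0.80); k = 0.7; accrual of 15, 25, 35, 45, 55, 70 and 90 per week. From Sections 9.1 and 9.3.4: two-sided test at 0.05. Assumption: the study cut-off falls 24 weeks after the last entry, at study week 39 + 24 = 63.

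**Accrual.** 3.5×15 + 4.5×(25+35+45+55+70) + 13×90 = 52.5 + 1035 + 1170 = 2257.5.

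**Follow-up cut to scheduled visits.**

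| Entry (study week) | Follow-up | Subjects | Share |
|---|---|---|---|
| 0 to 11 | 52 weeks | 270 | 12.0% |
| 11 to 27 | 36 weeks | 907.5 | 40.2% |
| 27 to 39 | 24 weeks | 1080 | 47.8% |

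The mean is 32.2 weeks. If each subject is instead followed continuously to the cut-off, up to 52 weeks, the mean is 37.8 weeks.

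**Formula.** The information per subject on the log rate is the average of μ/(1 + kμ), with μ = rate × years of follow-up. The variance of the log rate ratio is 1/(n·I₀) + 1/(n·I₁). Power = Φ(|ln 0.80|/SE − 1.960).

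**Cut to Weeks 24, 36 and 52.**
- Control: 0.478×0.561 + 0.402×0.703 + 0.120×0.833 = 0.651
- Triple: 0.478×0.487 + 0.402×0.624 + 0.120×0.755 = 0.574
- SE = √(1/(750×0.651) + 1/(750×0.574)) = 0.0661
- Power = Φ(0.2231/0.0661 − 1.960) = **0.921**

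**Continuous 24 to 52 weeks.** I₀ = 0.711, I₁ = 0.633, SE = 0.0631, power = **0.942**.

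A simulation of 2000 trials per case, with a maximum likelihood negative binomial fit, gave 0.923 (Monte Carlo SE 0.006) and 0.944 (0.005).

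**Which basis does the table use?** The rows for dispersion 0.7 and n = 750:

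| Control rate, reduction | Table | Cut to visits | Continuous |
|---|---|---|---|
| 1.50, 15% | 0.62 | 0.625 | 0.670 |
| 1.50, 20% | 0.87 | 0.872 | 0.904 |
| 1.50, 25% | 0.98 | 0.977 | 0.986 |
| 2.00, 15% | 0.70 | 0.699 | 0.738 |
| 2.00, 20% | 0.92 | 0.921 | 0.942 |
| 2.00, 25% | 0.99 | 0.991 | 0.995 |
| 2.50, 15% | 0.75 | 0.749 | 0.783 |
| 2.50, 20% | 0.95 | 0.948 | 0.962 |
| 2.50, 25% | >0.99 | 0.996 | 0.998 |

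The cut-to-visits column agrees with every row to about half a percentage point. The continuous column does not.

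**What 95% would take.** With follow-up cut to visits, 750 per arm reaches 95% power at a reduction of about 21.3%. At a 20% reduction it needs about 856 per pooled arm.

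**The case against.** The best defence is that Section 9.2.1 states its own basis, a variable duration of 24 to 52 weeks, and on that basis the power is 0.942, which is close to approximately 95%. On this reading nothing was miscalculated. The follow-up basis accounts for about two points (0.942 to 0.921), and the rest is 94% rounded up. The lower figure is also printed in the next subsection, and the sample size does not depend on it.

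All of that is fair as to cause and weight. It does not rescue the sentence, because continuous follow-up is not what Sections 4.2 and 5.7 prescribe, and Section 9.2.1 does not tell the reader that its basis differs from the table's. The word approximately does not bridge two figures that the table itself separates as 0.92 and 0.95.

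Two qualifications stand. First, the text of Section 9.2.2 does not spell out the visit-based follow-up; the link comes from the amendment rationale and the row-by-row match. Second, 0.92 is close to a ceiling. Section 5.7 puts the transition date more than 12 days before a completion date set 181 days after the last randomization, so at most 168 days (24 weeks) after it. If it fell 22, 20 or 16 weeks after the last randomization (assumed values), power would be about 0.915, 0.910 or 0.900. That moves further from 95%, not towards it.

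Also, 0.92 is the power of one comparison taken alone. The chance of success at Level 2 or Level 6 is lower, because every earlier test must succeed first.

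**Conclusion.** The concern holds and is minor. As written, Section 9.2.1 overstates the power for the key secondary endpoint by about three percentage points: 95% stated, 0.92 in the protocol's own table, 0.921 recomputed. The type II error for the single comparison is about 8%, not 5%.

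This rests on the planned 750 per pooled arm, the protocol's accrual schedule, a cut-off 24 weeks after the last entry, and no early withdrawal. SAP Section 5.4 lists 766 + 643 + 399 + 631 = 2439 randomized, or 813 per pooled arm. If the follow-up mix were unchanged (an assumption), that would give about 0.940. It does not make the statement about the planned sample size correct.

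Power stays above 90% at the planned size before any withdrawal. The primary endpoint, the sample size, the tests and the decision rules are unaffected.

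**What to change.** In Section 9.2.1, give the power as approximately 92%. State that it assumes follow-up ending at the Week 24, 36 and 52 visits, as in the Section 9.2.2 table, with no allowance for early withdrawal. The match to the table implies that no allowance was made, and the sponsor should confirm it.

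The protocol's 10% missing-data figure applies only to spirometry at Week 24. If withdrawal is to be reflected for exacerbations, label it as an assumption and give a range. For 10% withdrawal by Week 24, power is 0.893 if those subjects contribute no follow-up (n = 675 per arm) and 0.906 if they leave at a constant rate.

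The cost is one sentence of protocol text and a slightly less favourable stated figure. Sample size and conduct do not change.
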